Objective 2: G*Power software version 3.1.9.7 will be used to calculate the minimum required sample size to determine the pain scores of the ORAL7® Mouthwash group with the 0.2% chlorhexidine gluconate mouthwash group following surgical removal of mandibular third molars. The calculation will employ ANOVA for repeated measures with parameters including an effect size of 0.4 (as stated by Cunningham, 1978), a level of significance (α) of 0.05, a power ($1-\beta$) of 0.8, two groups, seven measurements, and a correlation of 0.5 among repeated measures. Based on these parameters, the total sample size required is calculated to be 32 participants.

Objective 3: G*Power software version 3.1.9.7 will be used to calculate the minimum required sample size to compare the mouth opening of the ORAL7® Mouthwash group with the 0.2% chlorhexidine gluconate mouthwash group following surgical removal of impacted mandibular third molars. The sample size will be estimated using an independent sample T-test with a two-tailed design, an effect size of 0.8 (as per Cunningham, 1978), a significance level (α) of 0.05, a power ($1-\beta$) of 0.8, and an allocation ratio of 1. Based on these parameters, the total sample size required is 52 patients, with 26 participants in each group.

The total sample size calculated based on all 3 objectives will be 52 patients. By anticipating 10% non-compliance and drop out of patients during this study, a final sample size of 58 patients will be included in this study and they will be randomized into 2 groups (interventional and control), with 29 patients in each group.

Research Tools and Variables

Research Tools

- a. Oral 7 mouthwash
- b. 0.2% chlorhexidine gluconate mouthwash
- c. SPSS software
- d. Landry wound healing index
- e. Visual analogue scale
- f. Metal ruler

Research Variables

- a. Demographic characteristic such as age, gender
- b. Angulation of impacted teeth
- c. Duration of surgery

Data collection method

This study is going to be conducted in the Oral and Maxillofacial surgery clinic of Hospital Pakar USM. Patients who require surgical removal of impacted mandibular third molar are enrolled and selected based on inclusion and exclusion criteria. Written informed consent to participate in the study will be taken from the subject without obligation. Informed consent can be withdrawn anytime by the subject throughout the study without penalty and continuation of care and treatment will not be affected.

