A list of random numbers will be generated for each group (total 58 numbers for 2 groups). Each group will have a set of 29 numbers. A container containing 58 papers with one written number on each will be prepared. Each participant will be instructed to draw a paper from the container before the surgical procedure commences. The number written in the paper will indicate the allocated group for the participant and as subject identification number.

Allocation concealment

The Dental Surgery Assistant (DSA) will identify the participants as control or interventional group, and mouthwash without label will be given to participants after completion of surgery.

Calibration

Intra and inter examiner calibration of Landry healing index will be conducted before study commences. It will consist of 2 sessions: alignment followed by assessment session. In this study, 2 examiners will be involved for assessment of Landry healing index score of surgical wounds after removal of impacted mandibular third molar.

Sample size for the calibration process will be calculated based on intraclass correlation, with 5 observations per subject, level of significance: 0.05, power: 0.8, minimum acceptable reliability: 0.6, expected reliability: 0.8, drop out 10% (Walter et al., 1998).

The sample size will be 28 for this study.

Calibration process will be repeated until full agreement is achieved between 2 examiners.

1) Alignment session

In this session, the Landry healing index will be explained. The clinical photographs of surgical site 1-week post-op with their respective Landry healing index scores are shown and explained. Agreement between 1st and 2nd examiner on the scoring will be obtained.

2) Assessment session

This session will begin after the alignment session. Subjects for assessment exercise will be recruited with entry criteria comparable to study subjects. Informed consent is obtained. Examiners will rotate among subjects to assess the surgical site of each subject and respective Landry healing index score is recorded.

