Total 2 rounds of examination are completed. Pairs of repeated scores are used to assess intra examiner reproducibility. Results will be analyzed using SPSS, intraclass correlation coefficient will be obtained and classified. Values less than 0.5 are indicative of poor reliability, values between 0.5 and 0.75 indicate moderate reliability, values between 0.75 and 0.9 indicate good reliability, and values greater than 0.90 indicate excellent reliability (Koo & Li, 2016). Assessment session will end when good or excellent reliability is obtained.

Clinical Procedures

Orthopantomogram (OPG) will be taken for routine pre-operative assessment. Cone beam computed tomography (CBCT) will be ordered if indicated. Written consent will be taken from patients. Mouth opening of the patients will be measured by using a metal ruler in millimeters from mesioincisal edge of upper right central incisor to mesioincisal edge of lower right central

incisor prior to surgery. Different relevant reference points can be taken if central incisor(s) is missing, and alternative points will be recorded in data collection form.

Patients will be disinfected and draped under standard procedure. All the surgeries will be performed by qualified operators under aseptic techniques. Local anesthesia will be achieved by administering inferior alveolar, long buccal, and lingual nerve blocks using 2 cartridges 2.2 ml of 2% Scandonest special (2% mepivacaine in 1:100,000 adrenaline).

Copious irrigation of the surgical site will be done using normal saline solution (40 ml) before the incision is made using no. 15 blade. A full mucoperiosteal envelope flap will be reflected. Buccal and distal bone guttering and the impacted mandibular third molar will be sectioned, when necessary, using surgical drill and normal saline irrigation, the tooth will be removed completely. Socket curettage and smoothing of sharp bony edges will be undertaken, flap and the extraction socket will be thoroughly irrigated with normal saline. Closure of the surgical wound will be done using 4-0 Vicryl suture. The duration of the surgery will be calculated from the time of incision till the last suture is given.

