Post-operative instructions will be given to the patient. The clinical research assistant will explain the instructions to the patients in Bahasa Malaysia. Patients will be instructed to start using the respective mouthwash (blinded from the principal investigator and patient) given on day 1 post op, in which one cup of about 10ml solution to be gargled for at least 30 seconds and then spit out. This is to be done 3 times per day for 1 week. Non-steroidal anti-inflammatory analgesic (capsule Celecoxib 200mg BD for 1 week) will be given to the patient. Rescue analgesic (tablet paracetamol 1000mg QID for 1 week) will be prescribed. No systemic antibiotics will be prescribed before or after the procedure. All patients will be requested to record their pain score and numbers of analgesics consumed, at 8am each day, for 7 days post operatively in each notebook.

Pain assessments are standardized at 08:00 hours each day to enhance methodological rigor and ensure temporal consistency across all participants. This fixed time point allows for standardization, thereby minimizing diurnal variation in pain perception and controlling for confounding influences related to circadian rhythms, physical activity, and analgesic pharmacodynamics. Recording pain at a uniform time facilitates comparability between subjects and across postoperative days, strengthening the internal validity of the dataset.

The choice of 08:00 hours specifically is informed by clinical and physiological considerations. It reflects a likely peak in discomfort following the waning effects of local anesthesia and overnight analgesia, capturing a more accurate baseline of spontaneous postoperative pain. Moreover, this time aligns with the routine clinical workflow, enabling synchronized follow-up assessments and promoting adherence among participants. Thus, the fixed 08:00 a.m. time point is not only methodologically sound but also pragmatically appropriate within the clinical setting of this study.

A review appointment 1 week after surgery for suture removal and examination for the assessment of pain score, mouth opening, and wound healing will be given to patients. These assessments will be performed by a blinded examiner after calibration with another expert.

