Pain will be measured by using visual analogue scale from 0 to 10. Mouth opening will be measured by metal ruler using the same reference points as preoperatively. Soft tissue healing of the surgical site will be investigated using the Landry Healing Index of Landry, Turnbull and Howley. This index is intended to assess healing of extraction sockets one week after intervention based on the following parameters: tissue color, bleeding response to palpation, presence of granulation tissue, characteristics of the incision margins and the presence of suppuration. Each wound can be scored from 1 (very poor healing) to 5 (excellent healing) (Marini et al., 2019).

The total duration of involvement of each patient will be 8 days starting from the day of the surgery till the 7th post-operative day that is the day for follow-up visit. The duration of the first visit that is the day on which the surgery will take place will depend entirely on factors like type and position of impaction, surgeon's experience, tooth morphology and root anatomy, patient factors like mouth opening, anxiety level, cooperation etc. and will usually take around 45 minutes for completion. The duration of the follow-up visit will be around 30 minutes. This is the standard time for each patient. In case of breakthrough pain which cannot be controlled by celecoxib and paracetamol, the patient will be instructed to contact one of the investigators as soon as possible as per the contact information given in the patient consent form which will be given to each patient participating.

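### The calibration claimed for the day-7 assessments covers the Landry index only, so it is unsupported for mouth opening (Objective 3); averaging replicate ruler readings would be a cheap gain in precision

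*Combined protocol and SAP*

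**What the plan says.** Mouth opening is the endpoint of the third specific objective and has its own sample size calculation. Under Sample Size Determination, Objective 3, this is an "independent sample T-test with a two-tailed design" with a standardized effect of 0.8, "a significance level (α) of 0.05", power 0.8 and equal allocation. It gives 26 per arm, 52 in total. Allowing for 10% non-compliance and dropout gives 58.

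Clinical Procedures describes the measurement. Before surgery, "Mouth opening of the patients will be measured by using a metal ruler in millimeters" between named edges of the upper and lower right central incisors, with substitute points noted if an incisor is missing. At one week, "Mouth opening will be measured by metal ruler using the same reference points as preoperatively". The review-visit paragraph names pain score, mouth opening and wound healing, and continues: "These assessments will be performed by a blinded examiner after calibration with another expert".

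The Calibration part of the Study flowchart opens with: "Intra and inter examiner calibration of Landry healing index will be conducted before study commences". Its alignment session uses photographs with Landry scores. In its assessment session the examiners score the surgical site. The intraclass correlation coefficient (ICC) and the rule for ending the session apply to those scores.

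**The concern.** Taken as written, the sentence in Clinical Procedures gives mouth opening a quality property that no described step provides. A report based on this plan would say that the Objective 3 readings were made after calibration, although the reproducibility of the ruler had not been examined.

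The plan also leaves open who takes the pre-operative reading, how many readings are taken on each occasion, and what reproducibility is acceptable. Random reading error adds to the standard deviation (SD) of mouth opening and so shrinks the standardized difference that the t-test can detect. What is at stake is some precision on a powered objective, and an accurate description of how its endpoint was measured.

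**Working it through.** **1. Compare the two descriptions.** In Clinical Procedures, calibration is claimed for all three review-visit assessments. In the Calibration text, the stated purpose, the photographs, the recorded score and the ICC all concern the Landry index. No other section adds a reproducibility check for the ruler. The two descriptions do not match for mouth opening.

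**2. Reproduce the planned size.** Inputs from Objective 3: d = 0.8, two-sided alpha 0.05, power 0.80, 1:1 allocation. For a two-sample t-test, the noncentrality is d·√(n/2) on 2n − 2 degrees of freedom.
- n = 26: 0.8·√13 = 2.884 on 50 df, power 80.7%.
- n = 25: power 79.1%.

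So 26 per arm (52) is the minimum, as stated. Dropout: 52/0.9 = 57.8, rounded up to 58, as stated.

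**3. Add reading error.** Let R be the reliability of one reading, that is, the share of its variance not due to reading error. The documents give no value, so R is an assumption. For scale, the error SD is √(1 − R) of the total SD: 0.22 at R = 0.95, 0.32 at 0.90 and 0.50 at 0.75. If errors are independent between readings, the mean of three has reliability R₃ = 3R/(1 + 2R) (Spearman–Brown).

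The plan does not say whether 0.8 refers to error-free values or to single readings, so both cases are shown.
- Case A, 0.8 includes single-reading error: d is 0.8 with one reading and 0.8·√(R₃/R) with the mean of three.
- Case B, 0.8 is error-free: d is 0.8·√R with one reading and 0.8·√R₃ with the mean of three.

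Power at 26 per arm, with d in brackets:

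| Assumed R | R₃ | A: one reading | A: mean of three | B: one reading | B: mean of three |
|---|---|---|---|---|---|
| 0.95 | 0.983 | 80.7% (0.800) | 82.0% (0.814) | 78.7% (0.780) | 80.1% (0.793) |
| 0.90 | 0.964 | 80.7% (0.800) | 83.3% (0.828) | 76.5% (0.759) | 79.3% (0.786) |
| 0.75 | 0.900 | 80.7% (0.800) | 87.3% (0.876) | 68.8% (0.693) | 76.5% (0.759) |

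The gain in case A is 1.3, 2.6 and 6.6 percentage points. In case B it is 1.4, 2.8 and 7.7 points. The value 0.75 is the lower edge of what the Calibration text calls good reliability.

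**4. Check for bias between arms.** If one examiner reads every patient at day 7 with a constant offset b, the difference between arms is (mean₁ + b) − (mean₂ + b) = mean₁ − mean₂. The offset cancels.

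**The case against.** **The sentence may be loosely worded.** It also covers pain on a visual analogue scale, which two examiners would hardly calibrate. It may mean only that the examiner is the person who completed the Landry calibration. That is plausible, but the sentence as it stands still extends the claim to mouth opening and needs correcting.

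**A reader might infer that Objective 3 has lost power.** The documents do not support this. They give no ruler reliability, SD or difference in millimetres. An effect size entered in a t-test is ordinarily the difference divided by the SD of the values analysed, so reading error may already be included. In that case nothing is lost against the plan, and the figures for three readings are a bonus.

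**A reader might infer that mouth opening is read only once per occasion.** The number of readings is not stated. The single-reading columns are an assumption.

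**A reader might infer that the readings are unstandardized or biased.** Instrument, unit, landmarks and their reuse at day 7 are all fixed. The day-7 examiner is blinded, and the pre-operative reading comes before the mouthwash is supplied. No bias between arms follows.

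**Calibration does not reduce random error.** This stands. Calibration mainly removes systematic differences between examiners, and an acceptance level of 0.75 would pass a ruler of only moderate precision. Replicate readings are what improve precision.

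**Timing.** The document is dated 16 October 2025, the study period began on 1 April 2025, and calibration was to come first. The session may already be over. This also stands, and it shapes the fix.

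**Conclusion.** The mismatch is established from the text: calibration is claimed for mouth opening but described for the Landry index only. It is a minor point of precision and documentation. The planned 52 and 58 reproduce and do not change.

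The size of any gain from replicate readings depends on an unknown R. It is about 1 to 3 percentage points of power if one reading has reliability of 0.90 or more, and about 7 to 8 points at 0.75. These figures assume one reading per occasion at present, errors that are independent between readings, and 26 evaluable patients per arm. Any error shared by the three readings would reduce the gain. Averaging cannot make precision worse, so it is worth adopting at its low cost even though no loss has been shown.

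**What to change.** 1. In both mouth-opening descriptions in Clinical Procedures (pre-operative and day 7), specify three ruler readings at each time point and analysis of their mean. State who takes them. The itemized list under Data collection method has no entry for mouth opening, so the form needs fields for the readings.
2. If the calibration session has not been held, add mouth opening to it with the same subjects, examiners and rounds, and report its ICC and its measurement error in millimetres. If the session is over, limit the calibration sentence in Clinical Procedures to the Landry index.

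The cost is protocol wording and a minute or two per visit, with no extra patients. If recruitment is under way, early patients may have fewer readings than later ones. The report should give the number of readings per patient.
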